2.7.1.5 Bath ankylosing spondylitis disease activity index 50% response (BASDAI50)

The subjects who achieve $\geq 50\%$ BASDAI score at post-Baseline from Baseline will be considered as BASDAI50 responders.

The proportion of subjects achieving the BASDAI50 response criteria at Week 12, Week 24 [REDACTED] will be analyzed by multiple logistic regression model with treatment and center as factors and weight and Baseline BASDAI as covariates.

2.7.1.6 AS disease activity score

The ASDAS-CRP (based on Quick-CRP) and ASDAS-ESR (Ankylosing Spondylitis Disease Activity Score) will be utilized to assess the disease activity status. Parameters used for the ASDAS include: total back pain (BASDAI question 2), the patient global assessment of disease activity (ASAS component 1), peripheral pain/swelling (BASDAI question 3), duration of morning stiffness (BASDAI question 6) and C-reactive protein (CRP) in mg/liter (or ESR) (Sieper et al 2009, Lukas et al 2009).

The ASDAS formulas are as follows:

$$\text{ASDAS-CRP/ ASDAS-quick CRP} = 0.121 \times \text{total back pain} + 0.110 \times \text{patient global} + 0.073 \times \text{peripheral pain/swelling} + 0.058 \times \text{duration of morning stiffness} + 0.579 \times \ln(\text{CRP} + 1).$$
$$\text{ASDAS-ESR} = 0.113 \times \text{patient global} + 0.293 \times \sqrt{\text{ESR}} + 0.086 \times \text{peripheral pain/swelling} + 0.069 \times \text{duration of morning stiffness} + 0.079 \times \text{total back pain}.$$

CRP is in mg/liter, ESR is in mm/h; the range of other variables is from 0 to 10; \ln represents the natural logarithm; \sqrt represents the square root. If any of the ASDAS components are missing ASDAS will not be calculated.

ASDAS (CRP) will be assessed by the investigator via eCRF at screening and Baseline for all patients in order to estimate the eligibility of the patient. Only patients with ASDAS > 2.1 will be enrolled. In addition, the ASDAS will be calculated via eCRF at Week 12 and Week 24 in order to estimate the response and to decide further treatment. Locally assessed quick CRP values will be used in order to evaluate disease activity for these purposes.

Disease activity states are inactive disease, low disease activity, high disease activity, and very high disease activity. The 3 values selected to separate these states were < 1.3 between inactive disease and low disease activity, < 2.1 between low disease activity and high disease activity, and > 3.5 between high disease activity and very high disease activity. Selected cutoffs for

improvement scores were a change of ≥ 1.1 unit for “minimal clinically important improvement” and a change of ≥ 2.0 units for “major improvement” ([Machado et al 2011](#), [Machado et al 2018](#)).

The number and percentage of patients in each of the categories will be presented for Baseline visit, Weeks 12, 24 and 36. The proportion of subjects meeting the ASDAS definition of inactive disease (< 1.3), ASDAS clinically important improvement (change from Baseline by ≥ 1.1), ASDAS major improvement (change from Baseline by ≥ 2) and ASDAS low disease activity (< 2.1) at Week 12, Week 24 [REDACTED] will be evaluated using a multiple logistic regression model with treatment group and center as factors and weight and Baseline ASDAS as covariates.

Furthermore, the ASDAS-CRP will be summarized descriptively (total score, change from Baseline) by treatment group and overall, at Week 12, Week 24 [REDACTED] for FAS. The between-treatment difference in change from Baseline in ASDAS will be evaluated using a MMRM. Treatment group and analysis visit as factors and Baseline ASDAS index score and weight as continuous covariates will be included in the model. Treatment group by analysis visit and Baseline ASDAS index score by analysis visit will be included as interaction terms in the model. An unstructured covariance matrix will be assumed. The treatment effect for the secukinumab T2T regimen at different analysis visits will be determined from the pairwise comparison performed between the 2 treatment groups.

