8.3.1.7 High sensitive Quick C-reactive protein test/ high sensitive C-reactive protein test

This assessment will be performed in order to identify the presence of inflammation, to determine its severity, and to monitor response to treatment. The quick hsCRP assessments will be performed locally at the study centers using a centrally provided assessment kit. The result of the quick hsCRP will be used to confirm eligibility of the patient (ASDAS ≥ 2.1 or CRP > 5 mg/L) at Screening and Baseline or to estimate further treatment of patients in the T2T arm at the Week 12 or Week 24 visit. In addition, the hsCRP assessment will be performed centrally as indicated in [Table 8-1](#) and used in final data analyses only.

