2.13 Other Exploratory analyses

Not applicable.

3 Sample size calculation

The sample size was calculated based on the primary efficacy variable ASAS40 response at Week 24 for the FAS. Available data from the DESIR cohort ([Molto et al 2014](#)) and the DANBIO registry ([Glintborg et al 2017](#)) showed an ASAS40 response of 30% in TNF α inhibitor naïve axSpA subjects, that were treated with common *biological* DMARDs.

Data from MEASURE 2/MEASURE 3 trials ([Sieper et al 2017](#), [Pavelka et al 2017](#)) showed an ASAS40 response of 43.2% and 43.9% at Week 16, while approximately 50% of subjects did not achieve an ASDAS clinically important improvement (defined as change from BSL of ≥ 1.1) criterion at Week 12. Taking into account the longer duration of active treatment with secukinumab 150 mg and the substantial proportion of subjects that will be escalated to 300 mg, it is justifiable to conservatively assume an ASAS40 response of 50% at Week 24.

With an ASAS40 response of 50% for the secukinumab 150 mg/300 mg arm and a 30% response in the SOC arm at Week 24 (corresponding to an OR of 2.3), 134 subjects per treatment arm are required to achieve a power of 90% to demonstrate superiority at a significance level of 0.05 using the 2-group continuity corrected χ^2 test of equal proportions.

In order to account for some uncertainties in the underlying assumptions and to compensate for some expected dropout and protocol violations, a total of 300 subjects (150 patients in the T2T and 150 patients in the SOC arm) should be randomized into this study.

4 Change to protocol specified analyses

Not applicable.

5 Appendix

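### The SAP builds the analysed ASDAS-CRP on the local quick CRP, while the protocol gives central hsCRP as the value for final analyses; the departure is undeclared and the SAP's own wording is inconsistent

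*SAP*

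**What the plan says.** **Protocol 8.3.1.7** describes two CRP tests. Of the one run at the site with a centrally supplied kit it says "The result of the quick hsCRP will be used to confirm eligibility of the patient" at Screening and Baseline, or "to estimate further treatment of patients in the T2T arm at the Week 12 or Week 24 visit". The central hsCRP is measured in addition, "and used in final data analyses only". Protocol 8.3.2 names ASDAS-CRP and ASDAS-ESR without tying the analysed score to either CRP test.

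**SAP 2.7.1.6** says three things about the source:

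- The opening sentence reads "The ASDAS-CRP (based on Quick-CRP" and sets this score beside ASDAS-ESR as the measures of disease activity.
- The formula carries a double label, "ASDAS-CRP/ ASDAS-quick CRP".
- After describing eligibility and the Week 12 and Week 24 treatment decisions, it adds: "Locally assessed quick CRP values will be used in order to evaluate disease activity for these purposes".

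The same section then sets out the analyses. The responder models begin with "The proportion of subjects meeting the ASDAS definition of inactive disease" and continue through the other three cut-offs, worded on ASDAS with no assay named. The descriptive summary is of ASDAS-CRP, and the MMRM is of change in ASDAS.

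**SAP section 4**, headed "4 Change to protocol specified analyses", records none.

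**The concern.** The protocol gives the two tests different jobs, and the SAP's only explicit definition of the analysed ASDAS-CRP uses the test that the protocol lists for the other job. A programmer following that definition would build the ASDAS-CRP family from a reading taken at the site in an open-label trial, although the protocol has a central measurement made for the analysis. A programmer who gave more weight to the later sentence on quick CRP, or to the protocol, would use the central value. The two could report different responder counts from the same database, each with some support in the text. Because section 4 reports no change, a reader of the study report would not learn that the source had moved.

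**Working it through.** **1. The plan's own figure.** The only design figure is 134 per arm for ASAS40 (50% against 30%, 90% power, two-sided 0.05, continuity-corrected chi-square).

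- Uncorrected: n' = [1.960 × √(2 × 0.4 × 0.6) + 1.2816 × √(0.25 + 0.21)]² / 0.2² = 124.
- Corrected: n = (124/4) × [1 + √(1 + 4/(124 × 0.2))]² = 133.8, so 134.

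This reproduces the plan. The four ASAS40 domains (SAP 2.5.1) are patient global, back pain, BASFI and morning stiffness. None contains CRP, so neither the primary outcome nor this figure depends on the choice of test.

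**2. The texts side by side.**

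| Use | Protocol 8.3.1.7 | SAP 2.7.1.6 |
|---|---|---|
| Eligibility | quick CRP | quick CRP |
| T2T decision, Weeks 12 and 24 | quick CRP | quick CRP |
| Analysed ASDAS-CRP | central hsCRP, as the final-analysis value | quick CRP in the opening definition; either, under the double label; no sentence assigns central hsCRP |

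The documents agree on the first two rows and conflict on the third.

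**3. Size of a change of source.** The CRP term in SAP 2.7.1.6 is 0.579 × ln(CRP + 1). Replacing the central value by the quick value at one visit shifts ASDAS by

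d = 0.579 × ln[(quick + 1)/(central + 1)].

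The documents give no paired readings, so the pairs below are assumed.

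| Quick (mg/L) | Central (mg/L) | Shift in ASDAS |
|---|---|---|
| 5 | 8 | 0.579 × ln(6/9) = −0.23 |
| 5 | 4 | 0.579 × ln(6/5) = +0.11 |
| 10 | 8 | 0.579 × ln(11/9) = +0.12 |
| 20 | 15 | 0.579 × ln(21/16) = +0.16 |
| 5 | 3 | 0.579 × ln(6/4) = +0.23 |
| 5 | 2 | 0.579 × ln(6/3) = +0.40 |
| 5 | 1 | 0.579 × ln(6/2) = +0.64 |

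A shift of 0.23 is 0.23/1.1 = 21% of the 1.1-unit response threshold. A shift of 0.1 needs CRP + 1 to differ by a factor of exp(0.1/0.579) = 1.19. The last rows would arise if the quick test could not report below 5 mg/L. The documents do not say so: 5 mg/L appears there as an eligibility and subgroup cut-off.

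**4. Which endpoints take the full shift.** The two state endpoints (below 1.3, below 2.1) take d at the visit concerned. The improvement endpoints take the difference, d at Baseline minus d at the visit. If (quick + 1)/(central + 1) is the same at both visits, the two cancel. If the 5-against-8 reading occurs at Baseline only, improvement is understated by 0.23. In either case only patients within that distance of a cut-off change status.

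**The case against.** The best defence is that the conflict is softer than it looks. In protocol 8.3.1.7 the restriction attaches to hsCRP: it limits hsCRP to the final analyses and does not expressly bar quick CRP from them. In the SAP, the later sentence confines quick CRP to eligibility and treatment decisions, the double label leaves room for a central version, and SAP 2.3.3 lists CRP and Quick CRP as separate Baseline variables. There is also a case for quick CRP on merit, since the analysed score would then be the one that drove T2T treatment.

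The first point stands as a matter of grammar, but the protocol still names central hsCRP as the analysis value. The second shows that the SAP is inconsistent; it does not show that the SAP is right, because no sentence assigns central hsCRP to an ASDAS endpoint. The third would be a reason to declare the departure in section 4, which has not been done.

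A reader might infer four stronger things that the documents do not support.

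- *A bias confined to T2T, because one reading error feeds both the decision and the endpoint.* Efficacy is assessed before dosing (protocol 6.7.2 and 8.3), so each visit's endpoint precedes that visit's switch. The Baseline value does carry from the Week 12 decision into the Week 24 endpoint, but nothing gives a direction or size. SOC treatment is also adjusted on disease activity (protocol 6.1).
- *That the central result is blind to arm.* Neither document says so, and the other four ASDAS components are patient-reported whichever assay is used.
- *That the primary model uses quick CRP.* SAP 2.5.2 and the code in 5.6.1 refer only to Baseline CRP; the source is unstated.
- *That SOC patients lack a quick CRP at Weeks 12 and 24 and would be counted as non-responders.* The Table 8-1 rows that would settle this are not in the text available.

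**Conclusion.** The concern holds in limited form. The SAP's definition of the analysed ASDAS-CRP conflicts with the protocol's allocation of the two tests, the change is not declared, and the SAP contradicts itself on the source. The reach is one secondary family at two visits: four responder endpoints and the change from Baseline, where these are read as ASDAS-CRP. SAP 2.6 states that there are no key secondary objectives, and the primary outcome and ASDAS-ESR are untouched.

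The size per patient follows from the SAP's own coefficient once a pair of readings is assumed: 0.11 to 0.64 in absolute value over the pairs shown. How many patients would change category cannot be derived, because the documents give no assay precision, reporting floor or CRP distribution. A simulated rate would reflect whatever values were put in. No direction of bias in the treatment comparison is shown.

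**What to change.** In SAP 2.7.1.6, state that ASDAS-CRP in all analysed endpoints, at Baseline and after Baseline, is derived from central hsCRP. Say which ASDAS version the four responder endpoints use, and separate the double-labelled formula into an analysed score and an operational score. Keep the quick-CRP score to describe the T2T decisions and as a sensitivity analysis of the same endpoints. In the same edit, name the source of the Baseline CRP covariate in SAP 2.5.2; this is a clarification, not a correction. If the sponsor prefers quick CRP for the analysis, the departure and its reason belong in section 4.

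The cost is SAP wording and one derivation. The protocol already provides for the central measurement, and neither data collection nor the handling of patients changes. One small downside is that a lost central sample makes ASDAS missing, since the SAP requires every component, and a missing response counts as non-response under SAP 2.7.3. The quick-CRP sensitivity analysis would show whether this matters.

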2.7.1.7 Bath ankylosing spondylitis functional index (BASFI)

The BASFI is a set of 10 questions designed to determine the degree of functional limitation in those patients with AS. The 10 questions were chosen with major input from patients with AS. The first 8 questions consider activities related to functional anatomy. The final 2 questions assess the patient’s ability to cope with everyday life. A 0 through 10 scale (captured as a continuous VAS) is used to answer the questions. The mean of the 10 scales gives the BASFI score – a value between 0 and 10. If there are missing questions the average of the non-missing items is used ([Braun et al 2009](#), [van Tubergen et al 2001](#)).

1. Put socks or tights without help or aids (0-10).
2. Bend to pick up pen without an aid (0-10).
3. Reaching high shelf without help or aids (0-10).
4. Up from armless chair without help (0-10).
5. Getting off from floor lying your back (0-10).
6. Standing 10 minutes without discomfort (0-10).
7. Steps without handrail or walking aid (0-10).
8. Looking shoulder without turning body (0-10).
9. Doing physically demanding activities (0-10).
10. Full day activities at home or work (0-10).

The BASFI will be summarized descriptively (total score, change from Baseline) by treatment group and overall, at Week 12, Week 24 [REDACTED] for FAS. The between-treatment difference in change from Baseline in BASFI will be evaluated using a MMRM. Treatment group and analysis visit as factors and Baseline BASFI score and weight as continuous covariates will be included in the model. Treatment group by analysis visit and Baseline BASFI score by analysis visit will be included as interaction terms in the model. An unstructured

covariance matrix will be assumed. The treatment effect for the secukinumab T2T regimen at different analysis visits will be determined from the pairwise comparison performed between the 2 treatment groups.

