2.5.1 Primary endpoint

The primary endpoint variable is the proportion of subjects achieving treatment response as defined by the ASAS40 criteria at Week 24.

ASAS responder: ASAS responder will be derived based on the following ASAS domains:

1. Patient's global assessment of disease activity measured on a VAS scale.
2. Patient's assessment of back pain, represented by either total or nocturnal pain scores, both measured on a VAS scale.
3. Function represented by BASFI average of 10 questions regarding ability to perform specific tasks as measured by VAS scale.
4. Inflammation represented by mean duration and severity of morning stiffness, represented by the average of the last 2 questions on the 6-question BASDAI as measured by a VAS scale.

Additional assessment domains:

5. Spinal mobility represented by the BASMI lateral spinal flexion assessment.
6. CRP (acute phase reactant).

ASAS response criteria 40% (ASAS 40): ASAS40 response is defined as an improvement of $\geq 40\%$ and ≥ 2 units on a scale of 10 in at least 3 of the 4 domains and no worsening at all in the remaining domain.

ASAS response criteria 20% (ASAS 20): ASAS20 response is defined as an improvement of $\geq 20\%$ and ≥ 1 unit on a scale of 0 to 10 in at least 3 of the 4 domains, and no worsening of $\geq 20\%$ and ≥ 1 unit at all in the remaining domain.

ASAS partial remission (PR): ASAS partial response is defined as a score of < 2 units on a scale of 10 for all 4 core ASAS domains.

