2.5.3 Handling of missing values/censoring/discontinuations

Subjects will be analyzed irrespective of adherence to assigned treatment regimen. Subjects without a valid ASAS40 assessment at Week 24 will be regarded as non-responders for the primary analysis.

In case of substantial missing data in the primary analysis, alternative approaches will be assessed by repeating the logistic regression model using ways to handle missing values. These may include, but are not limited to:

- Multiple imputation
- Observed data analysis

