2.7.1.4 Bath ankylosing spondylitis disease activity index (BASDAI)

The BASDAI consists of a 0 through 10 scale (0 being no problem and 10 being the worst problem, captured as a continuous VAS), which is used to answer 6 questions pertaining to the 5 major symptoms of AS:

1. Fatigue
2. Spinal pain
3. Joint pain/swelling
4. Areas of localized tenderness (called enthesitis, or inflammation of tendons and ligaments)
5. Morning stiffness severity
6. Morning stiffness duration

To give each symptom equal weighting, the mean (average) of the two scores relating to morning stiffness is taken and is then added to the sum of the first 4 questions. The resulting 0 to 50 score is divided by 5 to give a final 0 – 10 BASDAI score. BASDAI is a quick and simple index taking between 30 seconds and 2 minutes to complete. At least 4 questions should be non-missing to calculate the BASDAI score ([Haywood et al 2002](#)). Otherwise, BASDAI score will be missing. If Q5 and/or Q6 are missing or one of Q1 to Q4 is missing the total sum should be divided by 4 instead of 5. If two of Q1 to Q4 is missing and both Q5 and Q6 are not missing the sum should be divided by 3.

The BASDAI will be summarized descriptively (total score, change from Baseline) by treatment group and overall, at Week 12, Week 24 [REDACTED] for FAS. The between-treatment difference in change from Baseline in BASDAI will be also evaluated using a MMRM. Treatment group and analysis visit as factors and Baseline BASDAI score and weight as continuous covariates will be included in the model. Treatment group by analysis visit and Baseline BASDAI score by analysis visit will be included as interaction terms in the model. An unstructured covariance matrix will be assumed. The treatment effect for the secukinumab T2T regimen at different analysis visits will be determined from the pairwise comparison performed between the 2 treatment groups.

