2.7.1.14 Ankylosing spondylitis quality of life

The ASQoL is a self-administered questionnaire designed to assess health-related quality of life in adult patients with AS. The ASQoL contains 18 items with a dichotomous yes/no response

option. A single point is assigned for each “yes” response and no points for each “no” response resulting in overall scores that range from 0 (least severity) to 18 (highest severity). As such, lower scores indicate better quality of life. Items include an assessment of mobility/energy, self-care and mood/emotion. The recall period is “at the moment,” and the questionnaire requires approximately 6 minutes to complete. The purpose of the ASQoL is to assess the disease specific QoL of patients in this study.

At least 15 answered questions are required to be able to calculate ASQoL using mean imputation, (sum of answered)/(number answered)*18 ([Doward et al 2003](#)).

The ASQoL will be summarized descriptively (total score, change from Baseline) by treatment group and overall at Week 12, Week 24 [REDACTED] for FAS. Between-treatment differences in the change from Baseline in the ASQoL will be evaluated using a MMRM with treatment group and analysis visit as factors as well as Baseline ASQoL score and weight as continuous covariates. Treatment group by analysis visit and Baseline ASQoL by analysis visit will be included as interaction terms in the model. An unstructured covariance matrix will be assumed. The treatment effect for the secukinumab T2T regimen at different analysis visits will be determined from the pairwise comparison performed between the 2 treatment groups.

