2.7.1.15 Functional assessment of chronic illness therapy – fatigue

The Functional Assessment of Chronic Illness Therapy - Fatigue (FACIT-Fatigue©) is a 13-item questionnaire ([Cella et al 1993](#), [Yellen et al 1997](#)) that assesses self-reported fatigue and its impact upon daily activities and function. The purpose of FACIT-Fatigue in this study is to assess the impact of fatigue on patients with AS.

Subjects respond to each item on a 5-point Likert-type scale (0 = not at all; 1 = a little bit; 2 = somewhat; 3 = quite a bit; 4 = very much) based on their experience of fatigue during the past 2 weeks. The scale score is computed by summing the item scores, after reversing those items that are worded in the negative direction (i.e. original response of 0 gets mapped to 4, 1=3, 2=2, 3=1, and 4=0). Numbering the questions from 1 to 13, it is evident that questions 7 and 8 are worded in the positive direction (4 indicates a desirable response) and all other questions are worded in the negative directions (4 indicates an undesirable response). Thus, it is necessary to reverse the responses for all questions except 7 and 8 for scoring purposes. When there are missing item scores, the scale score was computed by summing the non-missing item scores, multiplying by 13 (the total number of items in the scale) and dividing by the number of non-missing items (i.e. normalizing the results). The latter rule applied only when at least half of the items (seven or more) are non-missing. FACIT Fatigue scale score range from 0 to 52, where higher scores represent less fatigue ([Cella et al 1993](#)).

The FACIT-Fatigue will be summarized descriptively (total score change from Baseline) by treatment group and overall at Week 12, Week 24 [REDACTED] for FAS. Between-treatment differences in the change from Baseline in the FACIT-Fatigue total score will be evaluated using a MMRM with treatment group and analysis visit as factors as well as Baseline FACIT-Fatigue score and weight as continuous covariates. Treatment group by analysis visit and Baseline FACIT-Fatigue score by analysis visit will be included as interaction terms in the model. An unstructured covariance matrix will be assumed. The treatment effect for the secukinumab T2T regimen at different analysis visits will be determined from the pairwise comparison performed between the 2 treatment groups.

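### BASFI, one of the four ASAS40 domains, is scored from however few items are answered; the SAP should set a minimum

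*SAP*

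**What the plan says.** SAP 2.7.1.7 defines the full score: "The mean of the 10 scales gives the BASFI score – a value between 0 and 10". For incomplete forms it adds: "If there are missing questions the average of the non-missing items is used". It cites two publications for this and gives no minimum. The protocol's BASFI section (8.3.1.3) has no missing-item rule.

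SAP 2.5.1 makes BASFI the third ASAS domain: "Function represented by BASFI average of 10 questions regarding ability to perform specific tasks as measured by VAS scale". ASAS40 requires at least 40% and at least 2 "units on a scale of 10 in at least 3 of the 4 domains and no worsening at all in the remaining domain". SAP 2.5.3 then says: "Subjects without a valid ASAS40 assessment at Week 24 will be regarded as non-responders for the primary analysis". Neither document defines a valid assessment.

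The comparable scores in the SAP each have a floor:

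- BASDAI (2.7.1.4): "At least 4 questions should be non-missing to calculate the BASDAI score", that is 4 of 6.
- ASAS-HI (2.7.1.12): at most 3 of 17 items missing.
- ASQoL (2.7.1.14): "At least 15 answered questions are required to be able to calculate ASQoL", that is 15 of 18.
- FACIT-Fatigue (2.7.1.15): prorated only "when at least half of the items (seven or more) are non-missing", that is 7 of 13.

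ASDAS and BASMI need every component (2.7.1.6, 2.7.1.8).

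Protocol 8.5.1 and Appendix 7 ask sites to check questionnaires for completeness and encourage missing answers. Appendix 7 also lets a site accept an incomplete form when the patient cannot finish it.

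**The concern.** The ten BASFI items differ in difficulty, from putting on socks to physically demanding activities. If only some are answered at Week 24, the mean covers different content from the Baseline mean, and the difference can reflect which items were skipped. ASAS40 then compares that difference with a fixed threshold in one direction and with zero in the other. A domain result could be wrong either way in a patient who did not change, and a nearly empty form could yield a score where non-responder imputation would otherwise apply. The planned multiple-imputation and observed-data analyses deal with missing assessments. A short-form BASFI is a non-missing score, so they would not reveal the problem. The same score also enters the BASFI repeated-measures model.

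**Working it through.** The plan gives no figure for BASFI completeness, so there is none to reproduce. The sample size of 134 per arm is unaffected.

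**1. Floors side by side.** BASDAI 4/6 = 67%; ASAS-HI 14/17 = 82%; ASQoL 15/18 = 83%; FACIT-Fatigue 7/13 = 54%. BASFI has none, so 1/10 is enough.

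**2. One illustrative record (assumed item scores).** Items 1 to 10 score 2, 3, 4, 4, 5, 5, 5, 6, 8, 8 at both visits. They sum to 50, so BASFI = 50/10 = 5.0 and the true change is 0. At Week 24:

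- Items 1-3 only: (2+3+4)/3 = 3.0. Change 2.0 units, 2.0/5.0 = 40%, so the domain threshold is met.
- Item 1 only: 2.0. Change 3.0 units, 60%, threshold met.
- Items 9-10 only: (8+8)/2 = 8.0. An apparent worsening of 3.0 units.
- Items 1-8 only: 34/8 = 4.25. Change 0.75 units, 15%, threshold not met.

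Enumerating every subset of this record, the threshold is met in 2 of 10 one-item sets, 3 of 45 two-item sets, 2 of 120 three-item sets, and no set of four or more items.

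**3. Random omission.** Assumptions: ten independent items, mean 5, kept within 0-10, no true change, items omitted at random at Week 24 only. Percentage of unchanged patients showing at least 40% and 2 units of improvement (simulation, 400,000 patients per setting):

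| Items answered | SD 1.5 | SD 2.0 | SD 2.5 |
|---|---|---|---|
| 1 | 7 | 13 | 19 |
| 2 | 1.5 | 4.8 | 8.4 |
| 3 | 0.2 | 1.5 | 3.5 |
| 5 | 0.0 | 0.04 | 0.3 |
| 7 or 8 | 0 | 0 | 0 |

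Other ways of generating items with this mean and SD move the one-item row by a few points, down to about 5% at SD 1.5. Hence about 5-19% overall.

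**4. What an 8-of-10 floor does to false improvement.** With a complete Baseline form, let the two omitted items average h and the other eight average l. Baseline = 0.8l + 0.2h and Week 24 = l, so the false improvement is 0.2(h - l). This reaches 2 units only if h = 10 and l = 0. If two different items are also missing at Baseline, the error is 0.25 times the gap between the two omitted pairs, so the gap must be at least 8 points.

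**5. What the floor does not do.** Any omission that leaves a higher mean counts as worsening. On the record above, skipping item 1 gives 48/9 = 5.33, and skipping items 1-2 gives 45/8 = 5.63. Of the single omissions, 4 of 10 score as worse; of the double omissions, 20 of 45 do. In the simulation about 50% of unchanged patients score as worse however many items are missing. The floor limits the size (at most 0.63 units on this record, against 3.0 without it), but the ASAS40 worsening condition ignores size.

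**6. From domain to endpoint.** A false BASFI improvement creates a responder only if exactly two other domains meet the threshold and the fourth has not worsened. A false worsening removes a responder only if the other three domains all meet the threshold.

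**The case against.** The strongest reply is that this will hardly ever matter. Under random omission, false improvement needs five or more missing items to occur at all often, and sites must check forms and prompt for missing answers. The record above is constructed: its scores rise in questionnaire order and the patient stops early. This largely stands. It limits the size of the problem, but Appendix 7 still allows incomplete forms, and the scoring rule has no backstop when one arrives.

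Second, SAP 2.7.1.13 accepts a single item for each multi-item SF-36 domain, so BASFI is not the only score with a low requirement. That is true. However, SF-36 uses model-based scoring, its summary scores need seven scales, and it does not feed ASAS40.

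Third, the BASFI rule is referenced, and the cited papers may set a minimum. That cannot be checked here; the SAP as written has none.

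Fourth, 8 of 10 is a choice. BASDAI and FACIT-Fatigue use lower proportions, and a floor of five would already hold random false improvement under 0.5%. This is fair. The case for eight is consistency with ASAS-HI and ASQoL, and protection when omissions are not random.

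A reader might infer that the SAP declares one-item forms valid. It does not: validity is undefined, and 2.5.1 describes the domain as an average of ten questions. The supportable statement is that nothing excludes such a form.

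**Conclusion.** The gap is real and minor. A rule feeding the primary endpoint has no completeness requirement, while the SAP's comparable averaged or prorated scores do. In unchanged patients the false domain improvement is about 5-19% with one item answered, under 0.5% with five and about 0% with seven or more. These rates assume mean 5, item SD 1.5 to 2.5 and random omission; they are rates per short form, not per trial patient. The documents give no frequency of short forms, and it is probably low.

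Two stronger readings are not supported. One is that the rule biases the trial towards one arm: nothing in the documents shows which arm would have more incomplete forms, or which items would be skipped. The other is that a floor alone cures the problem: it all but removes false improvement but leaves small false worsenings about as frequent as before.

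**What to change.** In SAP 2.7.1.7, replace the missing-item sentence with: *BASFI is the mean of the answered items if at least 8 of 10 are answered; otherwise BASFI is missing.* If ASAS40 then cannot be determined, the existing non-responder rule applies.

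To remove the false worsenings as well, add to SAP 2.5.1: *For ASAS40, the BASFI change is computed on the items answered at both Baseline and Week 24.* An unchanged patient then shows a change of exactly zero. With the floor applied at each visit, at least 8 + 8 - 10 = 6 items are shared.

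The cost is one or two sentences and a few lines of code. The downside is that a few incomplete forms become missing and may count as non-response.
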